**Table 8. Study measures to be completed by caregiver participants.**

Conceptual Model Domain	Measure	Number of Items	Completion Time
Antecedents			
Situational, sociodemographic, and relationship factors	Demographics	15	5 minutes
Contributions to Patient Self-Care			
Caregiver contributions to self-care	CC-SCHFI	22	8-10 minutes
Patient Symptom Experience			
Symptom prevalence and distress	MSAS-SF (Perceptions of Patients' Symptoms)	23	5 minutes
Depression	PHQ-2 (Perceptions of Patients' Depression)	2	1 minute
Depression/Burden			
Depression	PHQ-8	9	3 minutes
Subjective Caregiver Burden	ZBI-SF	12	4 minutes
Objective Caregiver Burden	DOBI	38	8-10 minutes
Quality of Life			
Relationship Quality	Mutuality Scale	15	5 minutes
Social Support	ESSI	7	3 minutes
Quality of Life	Benefit-Finding Scale	17	7 minutes

← Formatted Table

Data collection and management (Aims 1-3)

To ensure data integrity, the study protocol manual will include a section on data collection with descriptions of each data element or measure and instructions for its accurate collection or acceptable source. Several strategies will be used to avoid missing data and dropout, such as follow-up phone calls and letters. The study will use REDCap, a secure, HIPAA compliant, web-based application for building and managing online databases which is provided free of charge by the UCD CCTSI. All patients who are screened will be entered into one REDCap database that will store names, last four SSN (VA only) or medical record number (UCH and DH), eligibility and screening data, and contact information (phone numbers and addresses). There they will be assigned a study ID number that will link their information to the rest of their responses if they enroll in the study. A second REDCap database will contain patient and caregiver survey data and patient medical information. This database will not have any personal identifying information and will only be linked by study ID number. A third clinical database will be created in Microsoft Access that will be stored on secure VA servers with limited access. Only patients randomized to the intervention will be entered into this database, and it will store medical and visit data to track the process of the intervention. The data analyst will construct the study databases.

Monitoring plan

Monitoring will focus on recruitment, baseline comparability of treatment groups, protocol adherence, completeness of data, accrual of primary endpoint data, safety, and follow-up rates. This monitoring will provide the basis for reporting to a DSMB and quarterly review by the study investigators.

**Data Collection for Aims 4-6.**

Please refer to table 9 for a summary of data collection and analyses for Aims 4-6.

**Table 9:**

Study Aim	Data Source	Sample Size	Analytic Framework
AIM 4. Identify valuable core CASA intervention content and processes	Brief Patient Interviews	120	Qualitative analysis of patient and team member experiences on intervention content and structure (e.g., nurse, psychosocial care, care coordination with primary care provider), allowing for emergence of new codes/ideas
	CASA Patient Close Out Summary (one page each, data already collected as part of the CASA trial)	150	
	Focused Group Discussions with Intervention Team*	4-6	
AIM 5. Identify barriers and facilitators of CASA implementation and sustainability	Email Survey of Primary Care Providers Whose Patients Have Received CASA intervention	100	Qualitative analysis of data from multiple sites using the following CFIR Domains, Constructs , allowing for emergence of new codes/ideas
	Focused Group Discussions with Intervention Team*	4-6	Intervention Characteristics Relative advantage, complexity, cost, design quality and packaging
AIM 6. Determine interest and capacity of rural clinics to implement CASA's team-based model of outpatient palliative care	Interviews with Rural Health System Leaders and Providers	20	Characteristics of Individuals Knowledge & beliefs about Intervention Outer Setting Patients Needs and Resources Inner Setting Implementation climate, relative priority, readiness for implementation

← Formatted Table

Intervention evaluation data collection (Aims 4 & 5)

**Brief Interviews with Patients:** We will conduct brief in-person interviews with all willing patients in the CASA intervention arm who are completing endpoint measurement. Interviews will be conducted to elicit patient views about different parts of the intervention (e.g., nurse vs. social worker); how to improve the content and value of the intervention; communication and coordination; and whether and to what extent they continue to

Protocol: Improving Symptoms and Quality of Life in Chronic Heart Failure

PI: [name],

COMIRB #: 11-0969

sustain their use of CASA after the study. Value as defined by CHF patients is critical for ensuring CASA's patient centeredness. Interviews will be recorded with patient's consent.

**CASA Intervention Patient Close Out Summary:** As part of the CASA trial, the nurse and social worker complete a final "close out summary" on each patient once they complete the intervention. This 1-page summary form captures information on what worked well and not so well with components of CASA, what was missing, whether the patient engaged in and followed up with a goal (goal setting), and the likelihood that goal setting would continue. There will be approximately 150 close-out summaries to analyze.

**Interviews of Primary Care Providers:** We will administer a brief interview to select primary care providers who have patients who have completed the CASA intervention. Using a combination of rating scales and a few open-ended questions, the goal of these interviews is to efficiently identify strong positive or negative opinions about the usefulness of different CASA components, integration of CASA into work flow, and CASA's impact on quality of care. We will also ask for their insights into ways to sustain and spread CASA to other urban and rural sites.

**Focused Group Discussion with Intervention Team Members:** We will conduct several (2-3) structured group discussions with intervention team members to debrief about CASA implementation. The goal of these feedback sessions is to elicit intervention team views about what is and is not working well; what parts of CASA could be streamlined, dropped or enhanced; their views about patient, family caregiver, and primary care provider receptivity and responsiveness. Finally, we will ask team members about what it would take to scale-up and sustain a program like CASA as a regular service for patients with CHF within the current site and in rural sites and what should be included in an implementation toolkit. [name] will lead these focused group discussions which will be audiotaped and transcribed.

Rural feasibility data collection (Aim 6)

**Site Visits and Interviews with Rural Health System Leaders and Providers:** [name] will conduct site visits at rural clinics to explore their capacity to adapt, implement and sustain CASA. During the site visits, we will tour facilities and interview approximately four key leaders and providers at participating sites who have a role in decision making and planning for CASA implementation. Leaders and providers will be identified by key personnel at existing sites. Interview guides will use a combination of broad, open-ended questions to elicit leader/provider perceptions of CASA, using questions/probes guided by CFIR constructs. The questions are designed to improve our understanding of the facilitators and barriers to scaling up use of the CASA in rural areas, learning about their infrastructure and resources, current arrangements for palliative and psychosocial care, and how the CASA care model could be organized and implemented to improve quality of CHF care. We will learn how CASA fits within their organizational mission and priorities, meets a clear patient need, and might help them improve the quality of patient care. We will identify preferences around implementation processes to inform an implementation strategy. These interviews will be audiotaped and transcribed.

**Data Analysis Plan**

**Aim 1:** Assess the effect of a symptom management and psychosocial care intervention on heart failure-specific health status, measured by the KCCQ overall score, as a primary endpoint, and symptom distress, depression, quality of life, self-care, and spiritual well-being as pre-specified secondary endpoints.

Descriptive Statistics and Basic Comparisons

All analysis variables, both predictors and outcomes, will be examined carefully prior to any formal statistical analysis. Standard graphical methods, including histograms and boxplots, will be used to examine overall distributions and identify potential outliers, which will be confirmed prior to inclusion in analysis. Internal consistency of multi-item scales will be examined, and whenever possible, items and scales will be compared

Protocol: Improving Symptoms and Quality of Life in Chronic Heart Failure

PI: [name],

COMIRB #: 11-0969

to existing data to ensure appropriate performance within our HF population. Data transformations will be considered if indicated, such as log transformations for highly skewed data, to meet model assumptions. Each measure will be summarized using standard descriptive statistics, including means and standard deviations, medians, and ranges for continuous measures and proportions for categorical measures. Baseline characteristics will be compared between groups using appropriate exact nonparametric tests, such as Fisher's exact tests and Wilcoxon rank-sum tests.

#### Primary Analysis

Data from all participants will be included regardless of level of participation using an intent-to-treat approach. All outcome measures will be analyzed as continuous variables. Analyses of the repeated measures, including primary and secondary endpoints, will be performed using maximum likelihood estimation (MLE) for incomplete data (SAS Proc Mixed). This approach has several advantages: 1) all available data on eligible subjects can be included in the analysis even when there are missing data at follow-up, 2) MLE estimates the correlation between related measures and adjusts test statistics appropriately, 3) time varying covariates can be incorporated into the model, and 4) the assumptions about missing data are relaxed from Missing Completely at Random (MCAR) to Missing at Random (MAR). The primary analyses will not explicitly consider the pre-randomization variables unless there is a strong imbalance across the two groups, but the effect of these variables on outcome will be investigated as secondary analyses. Because missing data may occur as a result of morbidity or mortality, we will also perform sensitivity analyses utilizing auxiliary information such as BNP, hospitalization (with cause), outpatient/ED visits, and mortality to convert the missing data problem to a setting that is more likely to be MAR conditional on the auxiliary information.

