factors such as depression and spiritual well-being to quality of life over time is poorly described. *Examining the relative impact of different predictors of quality of life (e.g., spiritual well-being, HF self-care) will enable targeted approaches in subsequent interventions to improve quality of life in advanced HF.* This work will further refine our proposed intervention while informing the next generation of interventions.

Previous HF intervention studies do not measure or improve the large number of symptoms HF patients' experience, and prior palliative care interventions were unsuccessful, in part because of inadequate psychosocial care. We will test the *hypothesis* that an innovative, evidence-based, theory-driven symptom management and psychosocial care intervention will reduce symptom severity and depression in intervention patients compared to patients receiving usual care. We will test this hypothesis using a 3-site, 2-arm randomized, controlled trial (RCT) with outcome assessments at baseline, 3, 6, and 12 months in participants with a primary hospital diagnosis of HF that is advanced. The effect of the intervention on overall symptom severity and depression will be examined using linear mixed-effect models. The *rationale* for this aim is that if the intervention is successful, the research will contribute a patient-centered intervention that can be replicated, implemented, and disseminated in diverse health systems.

We plan to assess the effect of a symptom management and psychosocial care intervention on heart failure-specific health status as a primary endpoint. The study conceptual model and the proposed intervention effects are illustrated in **Figure 1**. The conceptual model is based on integrating elements of Lenz' unpleasant symptom theory into an adaptation of the Wilson and Cleary model of health related quality of life. Antecedent factors, the symptom experience, and depression/anxiety influence health-related quality of life. Heart failure-specific health status and spiritual well-being have been conceptualized as components of quality of life.

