**Figure 2. Study Design and Population Flow**

**Table 2. Study Participants' Accrual by Site**

Randomization

During a recruitment period of two years, 312 patients (13/month x 24 months) will be randomized to receive either the intervention or usual care. Randomization will occur at the patient level. The random allocation sequence will be computer generated using block sizes of 2-4, an allocation ratio of 1:1, and stratification by recruitment hospital. The allocation sequence will be concealed until after the last subject has completed the 12-month follow up and all of the data have been entered, re-checked, and finalized. [name], study statistician, will generate the allocation sequence and assign participants to the intervention and usual care groups.

	HF hospitalizations per month	Patients randomized per month
VA	18	5
UCH	40	6
DH	21	2
Total	79	13

Description of the Intervention and Control Groups

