9. FACIT-Sp: The Functional Assessment of Chronic Illness Therapy - Spiritual well-being scale (12 items; admin time 5 minutes) is a self-report measure that assesses overall spiritual well-being and includes subscales of meaning/peace and faith. It was developed and validated in a large sample of medically ill patients, many of whom had cancer, and has good psychometric characteristics in HF patients.

10. QUAL-E: The Quality of Life at the End of Life is a valid and reliable self-report measure of several domains, each scored separately, of quality of life in advanced illness. We will use the relationship with health care system, preparation, life completion, and global quality of life sub-scales (16 items total, administration time 8-10 minutes).

11. TICS: The Telephone Interview for Cognitive Status is an 11-item verbally administered test of cognitive status. The TICS takes approximately 4 minutes to administer and assesses memory and other cognitive functions. The TICS was originally developed to discriminate between cognitive normals and dementia patients and has demonstrated good sensitivity and specificity when discriminating between normals and individuals with mild cognitive impairment. The TICS will be used as a covariate in the analyses.

12. Control Preferences Scale: The Control Preferences scale is a one-item measure of patient preferences regarding participation in health-care decisions. Using a 5-point Likert-type scale ranging from patient-only decision-making to provider-only decision-making, patients rate the extent to which they want to be involved in their care.

Protocol: Improving Symptoms and Quality of Life in Chronic Heart Failure

PI: [name],

COMIRB #: 11-0969

13. GAD-7: The Generalized Anxiety Disorder-7 is an 8-item valid and reliable screening instrument for four common anxiety disorders in primary care (post-traumatic stress disorder, generalized anxiety disorder, panic disorder, and social anxiety disorder). It provides a continuous measure of anxiety symptoms.

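### The primary model's covariates hang on an undefined baseline imbalance, which leaves out the stratifying hospital and leaves the role of baseline KCCQ open

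*Protocol*

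**What the plan says.** The rule is in the Primary Analysis section under Aim 1: "The primary analyses will not explicitly consider the pre-randomization variables unless there is a strong imbalance across the two groups". The sentence continues: "but the effect of these variables on outcome will be investigated as secondary analyses". The analysis is a repeated-measures model fitted by maximum likelihood in SAS Proc Mixed, and the Data Analysis Plan defines the outcome as heart failure health status "measured by the KCCQ overall score, as a primary endpoint".

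Four other places bear on the rule:

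- **Randomization** is 1:1 with "stratification by recruitment hospital", at three sites. No section puts hospital in the primary model.
- **Descriptive Statistics and Basic Comparisons** states: "Baseline characteristics will be compared between groups using appropriate exact nonparametric tests". The protocol does not say whether these tests decide what counts as a strong imbalance.
- **Background and Significance** describes a trial "with outcome assessments at baseline, 3, 6, and 12 months", and Sample Size counts four assessments per completer. Baseline KCCQ may therefore be a modelled response rather than a covariate.
- **Measure 11 (TICS)** in the list of patient measures states: "The TICS will be used as a covariate in the analyses". It does not say which analyses.

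**The concern.** Covariates in a randomized comparison are best chosen in advance for their prognostic value. A rule that admits them only when the arms look different makes the primary model depend on observed data by arm. Here the rule has no threshold, no list of variables and no named decision-maker, so two competent analysts could follow it and arrive at different primary models.

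Hospital shows the difficulty most clearly. It is a pre-randomization variable, so the rule excludes it. Because allocation is stratified on it, the arms should be close to balanced within each hospital, and the trigger would rarely bring it back. Leaving a prognostic stratification factor out of the model tends to make standard errors too large.

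Baseline KCCQ is the other candidate, usually a strong predictor of later KCCQ. Depending on how the text is read, it is either absent from the model or present as a response whose arm means may differ at baseline. Neither reading is as efficient as fixed adjustment. What is at stake is precision the trial could have from data it already collects, and the assurance that the primary model was settled before the arms were compared.

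**Working it through.** **Inputs from the protocol (Sample Size; Randomization):** 312 randomized; 15% deaths plus 10% dropout; effect 0.4 SD; two-sided alpha 0.05; three hospitals.

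**Assumed, because the protocol gives no value:** baseline to follow-up KCCQ correlation r of 0.3, 0.5 and 0.7; share of outcome variance explained by hospital of 1% to 10%; equal variances; a single follow-up contrast among completers.

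**Step 1. Reproduce the plan's figure.** Completers per arm: 312 × 0.75 / 2 = 117. The noncentrality is 0.4 × √(117/2) = 3.059, and power is Φ(3.059 − 1.960) = 0.864. The noncentral t with 232 degrees of freedom gives 0.861. Both agree with the stated 86%, so that figure is the power of an unadjusted two-group comparison with no baseline or hospital term.

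**Step 2. Vary only the treatment of baseline KCCQ.** In units of the outcome SD, the working SD is √(1 − r²) with baseline adjustment and √(2(1 − r)) for a change from baseline with unconstrained arm means. The noncentrality is 3.059 divided by that SD.

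| r | SD, adjusted | Power, adjusted | SD, change | Power, change | Power, unadjusted |
|---|---|---|---|---|---|
| 0.3 | 0.954 | 0.894 | 1.183 | 0.734 | 0.864 |
| 0.5 | 0.866 | 0.942 | 1.000 | 0.864 | 0.864 |
| 0.7 | 0.714 | 0.990 | 0.775 | 0.977 | 0.864 |

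At r = 0.5, the adjusted analysis needs 87 completers per arm for 86% power, against 116 unadjusted: 116 × (1 − 0.25) = 87, a quarter fewer.

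**Step 3. Hospital alone.** If hospital explains a share R² of the variance, the SD is √(1 − R²). R² = 0.01 gives power 0.868 and R² = 0.10 gives 0.897, a gain of about 0.3 to 3 points over 0.864.

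**Step 4. Does the ranking survive a different contrast?** Suppose the contrast averages the three follow-up visits, with the same correlation of 0.3 between all visits and 0.4 SD at each. The variance of the average is (1 + 2 × 0.3)/3 = 0.533.

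- Unconstrained change: variance 0.533 + 1 − 0.6 = 0.933, SD 0.966, noncentrality 3.17, power about 0.88 to 0.89.
- Baseline-adjusted: variance 0.533 − 0.09 = 0.443, SD 0.666, noncentrality 4.59, power above 0.99.

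The levels move a good deal, but adjustment still does better.

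**Step 5. Error rate of an adjust-if-imbalanced rule.** The protocol gives no threshold, so one was assumed: adjust for baseline KCCQ only if a baseline test gives p < 0.05. With 40,000 simulated trials per setting and 117 per arm, rejection under the null was 0.043 at r = 0.5 and 0.036 at r = 0.7. With the trigger at p < 0.20 it was 0.038 and 0.026. Applied mechanically, such a rule is conservative.

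**The case against.** The strongest objection is that the protocol does not say baseline KCCQ is left out. Baseline is one of the four outcome assessments, the model is for repeated measures, and pre-randomization variables may mean the demographic and disease-severity variables listed under Additional Exploratory Analyses. That stands. A reader might infer that baseline KCCQ is excluded, but the text supports only that its role is unspecified. How its arm means are handled could reasonably be left to a statistical analysis plan.

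The power figures also rest on assumed correlations and on one follow-up visit among completers, whereas the planned model uses all available data and the protocol names no contrast. That stands too. Step 4 shows the levels shifting with the contrast, so the table illustrates a direction and a plausible size and does not measure this trial's loss.

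A reader might further infer that the rule inflates the false-positive rate. The documents do not support this, since the mechanical version is conservative. Simulated alpha reaches about 0.073 to 0.081 only if an analyst reports whichever of the adjusted and unadjusted models is significant, and no section plans that. Nor does the protocol tie the trigger to the baseline tests, which sit under descriptive statistics, so one cannot say how often it would fire.

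It is also tempting to read the TICS sentence as a contradiction. It refers to analyses in general, and the primary analysis rule sends such variables to secondary analyses, so the two can be reconciled. It is an ambiguity.

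The appeal to an unseen analysis plan does not dispose of the trigger. The protocol states the rule, and a plan that fixed one model would have to override it.

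**Conclusion.** The point holds in a limited form. The protocol makes the primary covariate set conditional on an undefined imbalance, the stratifying hospital is left out as a result, and the place of baseline KCCQ is not settled. These conclusions come from the text and need no assumed figures.

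The size is less certain. Under the single-follow-up assumptions, baseline adjustment is worth about 3, 8 and 13 power points over the unadjusted comparison at correlations of 0.3, 0.5 and 0.7. An unconstrained change contrast would fall below the protocol's own 86% at any correlation under 0.5. Hospital by itself adds little.

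A reader might conclude that the trial is underpowered. It is not on this ground, because the stated 86% is met by the unadjusted comparison. The finding is forgone precision plus avoidable discretion over the primary model. It is worth correcting while the model can still be fixed blind to outcome, but it is not a flaw that invalidates the design.

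**What to change.** In Primary Analysis, replace the conditional sentence with:

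> The primary model includes recruitment hospital and baseline KCCQ overall score (as a covariate, or as a response with baseline means constrained equal across arms), regardless of observed imbalance.

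Delete the imbalance trigger. Other pre-randomization variables can stay in the secondary analyses already planned. The descriptive baseline tests may remain, provided the text says that they do not drive the choice of model. In the TICS entry, state whether it is a covariate in the primary analysis or only in secondary analyses.

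The cost is a change of wording and about three model degrees of freedom: two for three hospitals and one for baseline KCCQ. No new data or additional patients are needed.
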